1.2 Endpoints

- 1.2.1 Primary: Ibrutinib plasma and chemokine concentrations, BTK occupancy by ibrutinib, BTK mRNA levels, BTK phospho- and total protein levels, downstream signaling, NF- κ B p65 levels and platelet functionality on days 1 (baseline), 8 and 28 of each cycle of treatment.
- 1.2.2 Secondary: Absolute lymphocyte count (ALC), hemoglobin and platelet levels, CLL-related symptoms, and palpable lymphadenopathy and/or hepatosplenomegaly on day 28 of each cycle of treatment; characterization of safety and tolerability of ibrutinib throughout the study.

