8 EVALUATION DURING STUDY

- 8.1 Physical examination along with evaluation of performance status, recording of AEs and concomitant medications on day 28 (± 2 days) of each cycle.
- 8.2 CBC and differential on day 28 (± 2 days) of each cycle.
- 8.3 Albumin, alkaline phosphatase, total, direct and indirect bilirubin, bicarbonate, BUN, calcium, chloride, creatinine, glucose, LDH, phosphorus, potassium, total protein, SGPT (ALT), SGOT (AST), and sodium on day 28 (± 2 days) of each cycle.
- 8.4 Serum beta-2-microglobulin and immunoglobulin levels (IgG, IgA, IgM) on day 28 (± 2 days) of each cycle.
- 8.5 ECG on day 28 (± 2 days) of each cycle.
- 8.6 Plasma concentrations of ibrutinib by high performance liquid chromatography with tandem mass spectrometric detection as previously described,⁶⁰ just before dosing and at 4 and 24 hours post-dosing on days 1, 8, and 28 (but before the first dose of the next cycle) of each cycle. Exception: there will be no 4-hour blood draw on day 28. Chemokines will also be measured, using enzyme-linked immunosorbent assay (ELISA).
- 8.7 BTK occupancy level by fluorescent affinity probe detection as previously described,^{9, 60} just before dosing and at 4 and 24 hours post-dosing on days 1, 8, and 28 (but before the first dose of the next cycle) of each cycle. Exception: there will be no 4-hour blood draw on day 28. See section 8.11.
- 8.8 Measurement of BTK mRNA and BTK and phospho-BTK protein and downstream signaling, as previously described,^{74, 75} just before dosing and at 4 and 24 hours post-dosing on days 1, 8, and 28 (but before the first dose of the next cycle) of each cycle. Exception: there will be no 4-hour blood draw on day 28.
- 8.9 Quantification of NF- κ B activation by ELISA as previously described,⁷⁶ just before dosing and at 4 and 24 hours post-dosing on days 1, 8, and 28 (but before the first dose of the next cycle) of each cycle. Exception: there will be no 4-hour blood draw on day 28.
- 8.10 Measurement of platelet functionality as previously described,⁷⁷ just before dosing and at 24 hours post-dosing on days 1 and 28 (but before the first dose of the next cycle) of each cycle.
- 8.11 Peripheral blood samples for plasma ibrutinib and cytokine levels, BTK occupancy, total and phospho-BTK mRNA and protein levels as well as levels of other downstream mediators of BCR signaling, and NF- κ B activity (appendix C) will be sent for processing to the laboratory of [name], Ph.D. at:

[name]
 [name]

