11 STATISTICAL CONSIDERATIONS

Ibrutinib is an inhibitor of Bruton's tyrosine kinase (BTK). The FDA has approved it for relapsed patients with CLL and frontline patients with del17p. Its standard dose is 420 mg/day (three 140-mg capsules). The primary objective of this pilot study is to determine the effects of different daily doses of ibrutinib (420 mg, 280 mg, 140 mg) on free drug levels in plasma, BTK occupancy by ibrutinib, BTK mRNA, BTK phospho- and total protein levels and NF- κ B activity. In total, 12 patients will be enrolled in this study. All patients will receive ibrutinib orally daily for 3 cycles. Each cycle will be 28 days long. In the first cycle, the daily dose of ibrutinib will be 420 mg (3 capsules), in the second cycle, 280 mg (2 capsules) and in the third cycle, 140 mg (1 capsule). That is, each patient will go through the three cycles with decreasing dose levels as described above. The half-life of ibrutinib is 4 to 6 hours and the drug does not accumulate after repeated oral dosing. Therefore, the influence of a previous cycle on the subsequent cycle is minimal.

Among the above pharmacokinetic and pharmacodynamic (PK/PD) parameters, a key factor is BTK occupancy. A dose level with BTK occupancy by ibrutinib $\geq 95\%$ (alternative hypothesis, H1) is regarded as sufficient, and that with an occupancy rate $< 85\%$ (null hypothesis, H0) is insufficient. Using a t-test to test H0 vs. H1, when the standard deviation of BTK occupancy rate (used as a continuous variable) is 0.10, a sample size of 10 to 12 patients can provide 80-88% power, at 2-sided significance level 0.05. This t-test will be conducted for each dose level. The data set described below shows that the standard deviation of BTK occupancy rate is about 5% when its mean is higher than 85%. As such, a sample size of 8 can provide 95% power at significance level 0.01. Therefore, even considering multiple testing adjusted by the Bonferroni method, and sample size reduction due to various reasons, this trial will still have sufficient power. An ideal dose level is sufficiently high to provide a high ($\geq 95\%$) BTK occupancy level by ibrutinib, but not higher, so that there is not much “left over drug” in plasma to cause toxicities, i.e, a low free drug level in plasma is desirable.

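### Does the BTK occupancy t-test need a named blood draw and a printed per-test alpha before its power statement can stand?

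*Combined protocol and SAP*

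**What the plan says.** Section 11 singles out BTK occupancy as a key factor. A dose is sufficient if occupancy is at least 95% and insufficient if it is below 85%. On the test it says: "This t-test will be conducted for each dose level". There are three dose levels (420, 280 and 140 mg), given in successive 28-day cycles to the same 12 patients.

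Two power statements follow. With an SD of 0.10, "a sample size of 10 to 12 patients can provide 80-88% power, at 2-sided significance level 0.05". Then: "The data set described below shows that the standard deviation of BTK occupancy rate is about 5% when its mean is higher than 85"%, so that "a sample size of 8 can provide 95% power at significance level 0.01". From these the section concludes that "even considering multiple testing adjusted by the Bonferroni method, and sample size reduction due to various reasons, this trial will still have sufficient power".

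Section 1.2.1 places the primary measurements "on days 1 (baseline), 8 and 28 of each cycle of treatment". Section 8.7 takes occupancy samples before dosing and "at 4 and 24 hours post-dosing on days 1, 8, and 28" of each cycle, then adds "Exception: there will be no 4-hour blood draw on day 28". The study calendar footnotes and Appendix C agree on the post-dose samples. Section 11 closes by listing occupancy among the variables to be summarised by mean (SD) and/or median (range).

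**The concern.** The plan has one formal hypothesis test, and two of its settings are left open.

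- **The draw.** There are 2 (day 1) + 2 (day 8) + 1 (day 28) = 5 post-dose samples per dose, and none is named as the tested value. They are not obviously interchangeable. The occupancy result cited from the phase I study is a 4-hour result, while day 28 has only a 24-hour sample. In cycles 2 and 3 the day 1 samples follow a single dose at the new level, after a full cycle at a higher one, with an irreversible inhibitor.
- **The alpha.** Section 11 mentions 0.05, then 0.01, then Bonferroni, without a number of tests or an adjusted level.

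If both were truly free, two analysts could follow the plan and disagree about whether a dose is sufficient. An analyst who picked the most favourable draw after seeing the data would call an insufficient dose sufficient more often than the adjustment for three doses allows.

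**Working it through.** **Inputs.** From Section 11: null boundary 85%, alternative 95% (difference 10 points), SD 10% or 5%, n = 8, 10 or 12, two-sided alpha 0.05 or 0.01, three dose levels. From Section 8.7, the calendar and Appendix C: five post-dose draws per dose. Correlations between draws and any true mean other than 85% or 95% are assumptions.

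**Formula.** For a one-sample t-test, power = P(T > t(1−α/2, n−1)), where T is noncentral t with n−1 degrees of freedom and noncentrality (difference/SD)·√n.

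**Step 1: the plan's own figures.**
- SD 10%, α = 0.05, n = 10: noncentrality (10/10)·√10 = 3.16, critical t 2.262, power 80.3%.
- SD 10%, α = 0.05, n = 12: noncentrality 3.46, critical t 2.201, power 88.3%.
- SD 5%, α = 0.01, n = 8: noncentrality (10/5)·√8 = 5.66, critical t 3.499, power 95.1%.

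All match. One-sided t (89.8%, 94.5%, 98.4%) and a two-sided normal approximation (88.5%, 93.4%, 99.9%) do not, so the 0.01 figure is also two-sided.

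**Step 2: the alpha that the text implies.** One test per dose level and three levels give 0.05/3 = 0.0167. The 0.01 is stricter than this, so the 95% quoted at 0.01 is a conservative check on the sentence that follows it.

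| True mean 95% | n = 8 | n = 10 | n = 12 |
|---|---|---|---|
| SD 5%, α = 0.05 | 99.8% | >99.9% | >99.9% |
| SD 5%, α = 0.0167 | 97.8% | 99.8% | >99.9% |
| SD 5%, α = 0.01 | 95.1% | 99.3% | 99.9% |
| SD 10%, α = 0.0167 | 44.7% | 60.4% | 72.9% |

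At SD 5% and a true mean of 95%, the verdicts at 0.05 and 0.0167 differ in 99.8 − 97.8 = 2.0% of trials at n = 8, and in fewer at larger n.

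**Step 3: where the alpha would matter.** The lowest passing observed mean is 85 + t·SD/√n. At n = 12 and SD 5% it is 85 + 2.201·5/√12 = 88.2% at 0.05, 85 + 2.820·5/√12 = 89.1% at 0.0167, and 85 + 3.106·5/√12 = 89.5% at 0.01. The disputed band is 1.3 points wide. With an assumed true mean of 90%, the verdicts at 0.05 and 0.0167 differ in 68.1 − 44.7 = 23%, 80.3 − 60.4 = 20% and 88.3 − 72.9 = 15% of trials at n = 8, 10 and 12. That mean lies between 85% and 95%, where the plan calls a dose neither sufficient nor insufficient.

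**Step 4: the draw.** Suppose every dose sits exactly at 85% at every draw, with α = 0.0167. With one fixed draw per dose, the chance of wrongly passing at least one dose is at most 3 × 0.0167/2 = 2.5%. By simulation, passing a dose on any of its five draws gives:

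| Correlation between draws (assumed) | n = 8 | n = 12 |
|---|---|---|
| 0 | 11.7% | 11.7% |
| 0.5 | 8.5% | 8.3% |
| 0.8 | 5.1% | 4.6% |
| 0.9 | 3.5% | 3.2% |

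Only an analyst who searches across draws incurs these rates. Fixing any one of the five beforehand keeps the 2.5% bound.

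**Step 5: the cap at 100%.** Normal theory is somewhat optimistic for a percentage with mean 95% and SD 5%. With a beta distribution of that mean and SD (an assumption), simulated power at 0.0167 is 90%, 95% and 98% at n = 8, 10 and 12. The claim of sufficient power survives.

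**The case for a change.** The strongest case for a change is that the plan commits to a test that labels a dose sufficient, so the tested quantity should be on paper before the data exist, and two sentences would put it there. No default draw can be read off with certainty: the 4-hour precedent is cited but not assigned to this test, and day 28 has no 4-hour sample. If true occupancy differed between draws (say 95% at one and 90% at another, SD 5%, α = 0.0167), the chance of passing would be 98% against 45% with 8 patients. The pilot label does not remove this, because the test is still planned.

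Part of this stands. The draw is unnamed and the adjusted alpha is unprinted, and the safe course is to settle both before the occupancy results are examined. The statement about power also rests on an SD of about 5%; Section 11 credits this to the phase I data set but prints no occupancy SD, dose or time point for it.

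The rest is weaker. The documents report no lower occupancy at 24 hours, so the 95%-against-90% contrast is hypothetical. The 11.7% false-pass rate needs zero correlation between repeated samples from the same patients, all three doses exactly at 85%, and a search across draws that no section proposes. Counting all 3 × 5 = 15 dose-by-draw tests has no basis in the text, which tests by dose level. Preferring one draw to another is a scientific choice on which the documents do not rule.

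**Conclusion.** No change is needed; this is missing detail that an analyst can fill sensibly. No stated figure or rule is wrong. Both power statements are correct, and the Bonferroni level follows from the text as 0.0167. Sufficient power holds at the plan's SD of 5%: 97.8% with 8 patients under normal theory, about 90% with a beta model. An analyst who fixes one draw per dose and adjusts for three doses has a sound test, with a familywise false-pass chance of at most 2.5%.

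The practical stake is also limited. This is a 12-patient pilot, no section ties the test to an action within the trial, Section 6.5 leaves treatment after cycle 3 to the physician, and Section 11 also weighs free drug level and summarises occupancy descriptively.

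The conclusion rests on the SD of about 5% and on the draw being settled before the results are seen. If the SD were 10%, power at 0.0167 would be 60% to 73% for 10 to 12 patients, and 80% would need 14. That would limit the power claim, but it would not invalidate the test.

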1. OBJECTIVES AND ENDPOINTS

1.1 Objectives

- 1.1.1 Primary: To determine the effects of different daily doses of ibrutinib (420 mg, 280 mg, 140 mg) on free drug and chemokine levels in plasma, BTK occupancy by ibrutinib, BTK mRNA, BTK phospho- and total protein levels, downstream signaling, NF- κ B activity and platelet functionality.
- 1.1.2 Secondary: To observe the effects of different daily doses of ibrutinib (420 mg, 280 mg, 140 mg) on clinical parameters in patients with CLL in terms of efficacy and safety.

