Previous clinical experience has shown that lower than standard doses of Ibrutinib have similar efficacy and lower toxicities. In a phase I study of ibrutinib in a different population of patients (with relapsed or refractory B-cell malignancies), BTK occupancy $\geq 95\%$ was achieved 4 hours post-dose in all patients receiving 2.5 mg/kg/day,⁶⁰ which equals 175 mg/day for patients weighing 70 kg. In total, 56 patients were enrolled onto this study with 7 dose levels, and 6 to 9 patients at each dose level, to provide data on means (SDs) of the concentration of ibrutinib over time, areas under the curves (AUCs) of the receiver operating characteristics (ROCs), BTK occupancy (in %) for different dose levels over time, and other PK/PD parameters. For the 7 dose levels, the mean AUCs over 0-24 hours range roughly from 100 to 1500 ng x h/mL, with their SDs ranging roughly from 20 to 400 ng x h/mL, and higher dose levels had larger mean AUCs and larger SDs. For the highest dose level, the mean (SD) concentrations of ibrutinib were roughly 20 (5), 100 (35), 135 (45), 55 (15) ng/mL at 1, 2, 3, and 4 hours after taking the drug. These data show that the sample sizes of 6 to 9 patients at each dose level are sufficient to provide reasonably accurate estimates for these PK/PD parameters. This pilot study will enroll up to 12 patients, but have each patient receive all the three proposed dose levels, one at a time, as described above.

We will also observe the effects of different daily doses of ibrutinib (420 mg, 280 mg, 140 mg) on clinical parameters in patients with CLL in terms of efficacy and safety. We will measure the absolute lymphocyte count (ALC), hemoglobin and platelet levels, CLL-related symptoms, and palpable lymphadenopathy and/or hepatosplenomegaly on day 28 of each cycle of treatment. We will characterize the safety and tolerability of ibrutinib throughout the study. Descriptive statistics will be used. Continuous variables e.g., clinical characteristics such as CBC parameters, and laboratory correlates such as plasma drug levels, BTK occupancy, mRNA and protein levels, and NF- κ B activity levels, will be summarized using the mean (SD) and/or median (range). Frequency tables will be used to summarize categorical variables.

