Measurement of platelet functionality: Syk protein activation will be evaluated in platelets isolated 24 hours post-treatment on days 1 and 28 of each cycle to determine if changes occur with different doses of ibrutinib during therapy.

Molecular profiling: The lymphocytes obtained in real-time during pre- and post-therapy will be saved and later sent for molecular profiling to determine a spectrum of total and phosphoproteins that have significance in CLL as well as in the B-cell receptor pathway.

BTK downstream pathway analysis: The leukemic lymphocytes will be washed, pelleted and saved to determine the decrease in target proteins BTK, pBTK (Tyr²²³) and downstream ERK, pERK(Thr²⁰²/Tyr²⁰⁴), AKT, pAKT (ser⁴⁷³) and NK-kB. Additional studies may be done to determine other downstream pathway molecules.

RT-PCR assays: To determine if changes in protein levels (identified during immunoblot assays) are due to changes in transcript levels, we will do RT-PCR assays on these samples.

References

1. Hallek M. Chronic lymphocytic leukemia: 2015 Update on diagnosis, risk stratification, and treatment. *Am J Hematol.* 2015;90(5):446-460.
4. Jain N and O'Brien S. Initial treatment of CLL: integrating biology and functional status. *Blood.* 2015;126(4):463-470.
8. Ponader S and Burger JA. Bruton's tyrosine kinase: from X-linked agammaglobulinemia toward targeted therapy for B-cell malignancies. *J Clin Oncol.* 2014;32(17):1830-1839.

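### Each patient takes all three doses, but Section 11 plans no within-patient confidence interval for a difference between doses (optional, low-cost improvement)

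*Combined protocol and SAP*

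**What the plan says.** Section 1.1.1 states the primary objective: "To determine the effects of different daily doses of ibrutinib (420 mg, 280 mg, 140 mg) on free drug and chemokine levels in plasma", and on BTK occupancy, BTK mRNA and protein, downstream signaling, NF-κB activity and platelet function. Section 11 gives the design as one that will "have each patient receive all the three proposed dose levels, one at a time", always in the same order: "each patient will go through the three cycles with decreasing dose levels as described above".

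Two analyses of the markers are planned, both in Section 11. BTK occupancy is tested against the 85% boundary, and "This t-test will be conducted for each dose level". Continuous laboratory markers, occupancy and plasma drug included, "will be summarized using the mean (SD) and/or median (range"). Section 11 adds that "a low free drug level in plasma is desirable" but sets no cut-off. Appendix C says that platelet Syk activation will be examined "to determine if changes occur with different doses of ibrutinib during therapy" and names no method.

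Neither Section 11 nor Appendix C plans a between-dose difference, a paired or mixed-model analysis, or a confidence interval.

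**The concern.** The t-test asks whether one dose is sufficient. It does not ask how a marker differs between doses, which is what the objective and Appendix C's platelet question ask. The other primary markers have only descriptive summaries.

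A reader given per-dose means and SDs can form an unpaired interval for a difference between doses. A paired interval needs the SD of the within-patient differences, which per-dose summaries do not contain. The text also allows median and range alone, in which case the mean difference can only be approximated. Sections 6.3 and 10 allow patients to stop before cycle 3 (no rate is given), so the per-dose summaries may come from partly different patients. At stake is how precisely and directly the between-dose part of the primary objective is answered.

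**Working it through.** **1. The plan's own figures.** One-sample two-sided t-test, noncentrality (difference/SD)·√n, difference 95% − 85% = 10 points:

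- SD 10%, alpha 0.05: power 80.3% (n = 10) and 88.3% (n = 12); Section 11 states 80-88%.
- SD 5%, alpha 0.01, n = 8: power 95.1%; Section 11 states 95%.

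Both reproduce. The sample-size arithmetic is sound, and the match confirms that each dose is compared with 85% and not with another dose.

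**2. Occupancy, 95% half-width for a difference between two doses, n = 12.** The SDs are Section 11's 10% and its second figure ("the standard deviation of BTK occupancy rate is about 5% when its mean is higher than 85"%). Equal SDs at each dose are assumed. The within-patient correlation ρ is not in the documents.

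- Unpaired: t(0.975, 22)·SD·√(2/12), with t = 2.074.
- Paired: t(0.975, 11)·SD·√(2(1−ρ)/12), with t = 2.201.

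| SD | unpaired | paired, ρ = 0 | ρ = 0.3 | ρ = 0.5 | ρ = 0.8 |
|---|---|---|---|---|---|
| 10 points | 8.5 | 9.0 | 7.5 | 6.4 | 4.0 |
| 5 points | 4.2 | 4.5 | 3.8 | 3.2 | 2.0 |

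Break-even is ρ = 1 − [t(2n−2)/t(n−1)]², which gives 0.11 at n = 12 and 0.18 at n = 8. These figures are for a simple paired t interval. A mixed model pools variance over the three doses and would give a somewhat different width.

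**3. Plasma drug, 95% CI factor on a ratio of doses.** Log-SD = √ln(1+CV²). Unpaired factor = exp[t(2n−2)·log-SD·√(2/n)]. For the paired factor, use t(n−1) and √(2(1−ρ)/n). Dose-proportional exposure is assumed, so the true ratios are 420/280 = 1.5 and 420/140 = 3.

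| Source of CV | CV | log-SD | unpaired factor, n = 12 | paired, ρ = 0.5 | 1.5 ÷ unpaired | 3 ÷ unpaired |
|---|---|---|---|---|---|---|
| 4-hour concentration 55 (15) ng/mL, top phase I dose, Section 11 | 27% | 0.268 | 1.25 | 1.19 | 1.20 | 2.39 |
| AUC 1445 ± 869, Section 4.8 | 60% | 0.556 | 1.60 | 1.42 | 0.94 | 1.87 |
| AUC 680 ± 517 at 420 mg, Section 4.4 | 76% | 0.675 | 1.77 | 1.54 | 0.85 | 1.69 |

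The 3-fold step excludes 1 unpaired at every CV. At 27% the 1.5-fold step does too, and still does with 8 patients (1.5/1.33 = 1.13). At 60% or 76% the unpaired interval for the 1.5-fold step includes 1. A paired one excludes it only when ρ exceeds 1 − (n/2)·[ln 1.5/(t(n−1)·log-SD)]², which is 0.34 (CV 60%) or 0.55 (CV 76%) at n = 12, and 0.62 or 0.74 at n = 8. At CV 76% and ρ = 0.5 the paired lower limit is 1.5/1.536 = 0.98, so 1 is still included.

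**4. Sampling time for plasma drug.** With the stated half-life of 4 to 6 hours, the fraction left at 24 hours is 0.5^(24/4) = 1.6% to 0.5^(24/6) = 6.3%. Section 8.6 and the study calendar schedule a 4-hour draw on days 1 and 8 of every cycle and none on day 28.

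**The case against.** The strongest reply is that this is a small pilot with one formal decision, which a between-dose interval does not touch, and that the benefit is uncertain. Most of that stands. The gain depends on a correlation that the documents do not give. If occupancy sits near its ceiling at more than one dose, which the phase I data in Section 3 make plausible, then equal SDs and ρ = 0.5 are doubtful. Section 4.4 already says that exposure rises with dose, so an interval confirming that 280 mg gives less drug than 420 mg would add little.

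The fixed descending order is a second limit. Section 3 expects total BTK protein to fall during therapy, so a within-patient contrast carries time on treatment as well as dose. Section 11's half-life argument concerns leftover drug and does not remove this. A narrower interval does not remove it either.

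Two stronger readings are tempting, and the documents do not support them.

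- A reader might infer that the plan yields no estimate at all of how doses differ. With complete data, the difference between two reported per-dose means equals the mean within-patient difference. Only its paired interval is missing.
- A reader might infer that, without a cut-off in Section 11, plasma drug at one dose can be judged only against another dose. The background gives reference values: an AUC of 160 ng x h/ml in Section 3, and 78 nM for TEC in Section 2.4, about 34 ng/mL (78 nM × 440.50 g/mol). Section 11 does not adopt either as a criterion, but they exist.

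What survives the objection is that the natural summary of a within-patient design is absent and cannot be rebuilt from the planned tables.

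**Conclusion.** The omission is certain; its consequence is modest. The plan lacks a paired interval for any between-dose difference, and with medians only or early leavers even the point difference is approximate or not wholly within-patient. The gain for occupancy is about 25% in interval width at n = 12 if ρ is 0.5 and SDs are equal, and a paired t interval gains nothing below ρ of about 0.11. For plasma drug, pairing could change a conclusion only for the 1.5-fold step, only if the CV is nearer the AUC figures (60-76%) than the 4-hour figure (27%), and only if ρ exceeds about 0.34 to 0.55 with 12 patients. That rests on dose-proportional exposure, and AUC variability is only a proxy for that of a single concentration.

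It would be wrong to infer that the test against 85%, its power, or the dose-sufficiency decision is undermined. They are unaffected. This is an optional, cheap improvement.

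**What to change.** Keep the per-dose t-test against 85%. Add to Section 11, for example:

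*For each primary marker, at one pre-named sampling time available in every cycle (for plasma drug, a 4-hour draw on day 1 or day 8), within-patient 280-versus-420 and 140-versus-420 differences (ratios on the log scale for concentrations) will be reported with 95% CIs from a mixed model with dose as fixed and patient as random effect, using all available data. Because dose order is fixed, each contrast reflects dose plus time on treatment, notably for BTK protein, which is expected to fall during therapy; contrasts are estimates, not formal tests.*

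The sponsor would choose the sampling time for each marker and say whether contrasts use planned or actual dose. The cost is two sentences, those choices and a little more analysis work. No patients, visits or assays are added.
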